## **Risks associated with study**

### **a. Risks associated with PRP**

Intra-articular injections have been proposed to be a safe procedure, with low complication rate, if performed while taking adequate precautions [34]. The risks related to the intra-articular injections are infection, with an incidence of 1 in 50,000 inoculations, pain at the injection site, and erythema.

Intra-articular injections with PRP, as with every intra articular injection (and not due to the PRP itself) can result in cutaneous rashes or urticaria, pain at the injection site, or erythema, all of which are considered very rare based on previous level 1 studies [3, 8, 9]. Pain, swelling, redness, warmth, and bruising at the injection site or headache may occur, all which are rather rare.

As with every joint injection, a joint infection could potentially occur.

### **b. Risks Associated with dGEMRIC MRI and Non-contrast MRIs**

The initial MRI performed for this study is considered standard of care in the management of knee osteochondritis dissecans. The follow-up MRI at 6 months is for research purposes.

If a patient receives a dGEMRIC MRI, the gadolinium based contrast agents used for this type of imaging can result in nausea, vomiting, cutaneous rashes, shortness of breath, or chest pain, all of which are considered very rare [35]. Death attributed to gadolinium based contrast agents is extremely rare, “The overall rate of gadolinium-based contrast agent deaths reported to the FDA Medwatch database is less than 1 in a million (40 deaths in 51 million administrations), similar to the risk of death from a chest radiograph, drinking one half liter of wine, smoking 1.4 cigarettes ([tobaccodocuments.org/lor/03732381-2387.html](http://tobaccodocuments.org/lor/03732381-2387.html)), or traveling 86 miles by car ([www-nrd.nhtsa.dot.gov/Pubs/811291.PDF](http://www-nrd.nhtsa.dot.gov/Pubs/811291.PDF)).”

The specific gadolinium based contrast agent used at Children’s Hospital Colorado, gadobenate dimeglumine (MultiHance), was recently evaluated for safety in children without any adverse effects observed during the first twenty-four hours after contrast administration [36].

Nephrogenic systemic fibrosis is a fibrosing disorder associated with exposure to gadolinium-based contrast agents in people with severely compromised renal function [36]. There have been seventeen documented cases in patients 18 years or younger with documented exposure to gadolinium-based contrast agents [37]. Proposed risk factors are dialysis patients with GFR below 30 mL/min, high-dose gadolinium, proinflammatory conditions, acute renal failure, postoperative state, and hyperphosphataemia. The American College of Radiology recommends that people with severe chronic kidney disease (eGFR <30 mL/min/1.73 m^2) or acute kidney injury should avoid exposure to gadolinium-based contrast agents. The American College of Radiology recommends that people with severe chronic kidney disease (eGFR <30 mL/min/1.73 m^2) or acute kidney injury should avoid exposure to gadolinium-based contrast agents [37].

Risk which apply to either dGEMRIC or Non-contrast MRIs: There are no major risks associated with the magnetic fields and radio waves associated with extremity MRI. Rarely, one in thousands of exams, a sunburn-like skin burn might occur over a small area of the body, but special precautions are taken to avoid this. The patient must lie still in a small space which could create stress or anxiety. The patient might also feel cold because the MRI scanner room is kept cool, but blankets can be provided. The scanner makes a loud knocking noise when it is operating, but earplugs or headphones can be worn. Expected adverse events include stress/anxiety, claustrophobia, discomfort, or having a non-diagnostic study as a result of motion artifact. Some patients are unable to hold adequately still resulting in motion artifact on the images which could deem them uninterruptable. The amount of motion artifact for this to occur would have to be extensive, and will therefore most likely occur in few study participants, if any.

### **c. Complications and Pain associated with Study**

Follow-up visits will take place on the CHCO main campus or one of the following satellite locations (South, Parker, Centennial, Uptown/St Joseph's or Broomfield). All PRP injections will be performed at Children's Hospital Colorado. The clinic, being a well-equipped outpatient facility, has additional rescue devices. Adverse events and pain medications used will be reported and monitored by [name]/[name] or their colleagues during each follow-up visit using the electronic medical records clinical encounter notes. Patients are reminded to contact [name]/[name] or [name] with questions or to discuss adverse events they might sustain.

We will assist in arranging care for any injuries patients may sustain by participating in this study. However patient's insurance will be billed for any care that is provided.

### **d. Recording and Reporting Adverse Events**

The study investigators will monitor all subjects enrolled for any potential adverse effects (AE) associated with the treatments provided. Clinically significant results will be reported as adverse events and will be graded on a three- point scale (mild, moderate, and severe)[38]. In the event that AE occurs the following will be documented and reported to the IRB:

- Nature of adverse effect.
- Clinically significant adverse events will be graded on a three- point scale (mild, moderate, severe)
- Statement as to why it is considered unanticipated or anticipated but with change in nature or severity or frequency of occurrence from baseline
- Statement as to the degree to which it is considered treatment related (unrelated, remote, possible, probable), and why.
- Results of any diagnostic tests that were performed
- Description of any treatment implemented
- Statement of subject's current clinical status
- Investigator's signature and date.

Local side effects and irritations such as cutaneous rashes or urticaria, painful injection site, local heat, swelling, painful knee, and erythema will be recorded.

The investigator will supply a report for COMIRB if the adverse effects are unanticipated or if anticipated adverse effects change in intensity, frequency, or duration.

## **Safety Measurements**

The nature, onset, duration, severity, and outcome of all adverse events, as well as any association of an adverse event related to the study medication, will be assessed and documented at each visit. Patients will be asked to avoid intake of NSAIDs. If symptoms require pain medications during the initial follow up period (6 months after last injection), NSAID consumption will be recorded, as well as other pain medications taken. Patients will be allowed to have non-NSAIDs rescue medication as needed to treat pain. This includes acetaminophen and in select cases opioids such as Vicodin or Percocet. To evaluate the safety profile of the treatments, all complications and/or adverse events will be reported with their level of severity and their causal relationship to the study treatment.

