Battaglia et al recently reported the outcomes of injection of PRP for OA of the hip. Twenty patients, with a mean age of 52 years, who presented symptomatic OA of the hip were treated with a total of 3 intrarticular injections of PRP. Patients were prospectively evaluated at 1, 3, 6, and 12 months follow up. All patients had significantly improved clinical symptoms. No major complications or adverse events occurred at the moment of injection or in the follow-up period. Ten patients reported a slight pain during or after the injection, which spontaneously resolved in 1 or 2 days [30].

Gillis et al evaluated autologous chondrocyte transplantation in patients with full thickness chondral lesions of the knee utilizing dGEMRIC to indirectly quantify the GAG content of cartilage at the site of transplant, adjacent to the site of transplant, and distant to the site of transplant. The study demonstrated that GAG levels in grafts that had been implanted at 12 months or greater had GAG levels comparable to adjacent and remote cartilage. [31]

Typically, patients with Juvenile Osteochondritis Dessicans will heal without treatment within a 12 month period, therefore it was recently decided that the research dGEMRIC MRI would be performed 6 months from the time of the consent instead of 12 months. [32]

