### **PRP and Conservative Treatment Schedules Following Randomization**

Patients will be assessed during a standard of care visit for basic eligibility to participate in this study or via a telephone call with one of the Study Team Physicians. Patients who meet the basic inclusion criteria will be given the option of participating in the study either at this first visit, or a subsequent visit after they are given the opportunity to review the informed consent documents.

**PRP study participants:** A total of 8 visits (9 visits, if consent is done as a separate visit) are expected during a 12-month time period for patient follow up. All initial visits will include a patient assessment using basic standard of care to determine eligibility for study enrollment. This first visit, if the patient decides to enroll, may also include patient consenting. The second through fourth visits, one week apart +/- 10 days, will include treatment with PRP injections. After the 3rd injection, subjects will be seen for clinical evaluation and survey assessment per schedule of assessment below as the standard of care. MRI obtained prior to enrollment for initial evaluation of the knee is performed as standard of care in the management of knee OCD. The research MRI performed at 6 months post treatment will be obtained to assess cartilage healing utilizing physiologic imaging of cartilage with the dGEMRIC technique or a Non-contrast MRI of the knee.

The three injection visits (1 through 3) will take approximately 30-45 minutes per visit. This includes time for the baseline patient reported outcomes and blood draw.

Follow up visits (5 through 9) last around 30 minutes and will include patient reported surveys, physical examination, and x-rays to assess the injury in accordance with the standard of care at CHCO.

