**Conservative treatment participants:** A total of 5 visits (6 visits, if consent is done as a separate visit) are expected during a 12-month time period for patient follow-up. The first visit will include initial assessment and possible recruitment. The second through fifth visits will include patient reported surveys, physical examination and x-rays to assess the injury in accordance with the standard of care at CHCO. MRI obtained prior to enrollment for initial evaluation of the knee is performed as standard of care in the management of knee OCD. The research MRI performed at 6 months post treatment will be obtained to assess cartilage healing utilizing physiologic imaging of cartilage with the dGEMRIC technique or a Non-contrast MRI of the knee. **Please refer to the patient schedule matrix, Table 3, below.**

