## **Informational patient brochure/Compliance Surveys/ Baseline and Follow-up KOOS and IKDC surveys/Clinical Assessments**

An informational brochure (see attached) will be used to assist in the recruitment of eligible patients. The brochure will describe the autologous platelet rich plasma treatment, process, risks, appointment information and post procedure information.

Patients randomized to the PRP Treatment arm will receive a Pre and Post-Injection Instruction handout (see attached). The handout describes how the patient should prepare for the PRP injections and what to expect after the injection.

The study personnel who consents the patient will request the patient's and parent's email addresses which will be used to send out the weekly and monthly surveys.

For the first 6 weeks of the study, all patients will receive a weekly Compliance Survey (see attached) created by the Sports Medicine physicians to validate compliance with 1. non-weight bearing, 2. wearing a brace, 3. at home PT exercises, and 4. no high impact activity.

**KOOS/IKDC surveys:** All patients will receive a baseline survey and repeat surveys at 6 wks, 12 wks, 6 m, 9m, and 12 months, which is considered standard of care, on the CHCO main campus or one of the following satellite locations (South, Parker, Centennial, Uptown/St Joseph's or Broomfield). The surveys will include the following outcome scales: Pedi IKDC and KOOS-child.

The Pedi-IKDC is a modified version of the widely used International Knee Documentation Committee (IKDC) Subjective Knee Form, which is a knee specific measure of symptoms, function and sports activity. The Pedi-IKDC was developed for use with children and adolescents ages 10-17. The reliability and validity of the Pedi-IKDC has been demonstrated to be acceptable in young patients with a variety of knee disorders.

Similarly, the KOOS – child is a pediatric version of the Knee Injury and Osteoarthritis Outcome Score (KOOS). The KOOS-child score is subdivided and scored in five categories: Pain, Other Disease-Specific Symptoms, Activities of Daily Living Function (ADL), Sport and Recreation Function and Knee-related Quality of Life (QOL).

[http://www.actaorthop.org/sup\\_files/5292.pdf](http://www.actaorthop.org/sup_files/5292.pdf)

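### Adverse event collection is tied to visits under two rules that disagree: one gives unequal early ascertainment by arm, the other leaves the injection weeks uncovered, and under both, reactions to the third injection wait until about week 6

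*Combined protocol and SAP*

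**What the plan says.** Safety Measurements sets the main rule: "The nature, onset, duration, severity, and outcome of all adverse events", together with "any association of an adverse event related to the study medication, will be assessed and documented at each visit". Section c (Complications and Pain associated with Study) gives another: adverse events and pain medications are monitored "during each follow-up visit using the electronic medical records clinical encounter notes". For the PRP arm, the protocol reserves the term follow-up visits for visits 5 to 9, after the injections, so the two rules do not cover the same occasions.

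The visit schedules differ by arm. PRP patients have "A total of 8 visits (9 visits, if consent is done as a separate visit"), and "The second through fourth visits, one week apart +/- 10 days, will include treatment with PRP injections". Footnote C to Table 3 adds a PRP-only physical examination before each injection. Controls have 5 visits (6 with separate consent): a first visit for assessment and possible recruitment, after which "The second through fifth visits will include patient reported surveys, physical examination and x-rays to assess the injury". The first scheduled clinical follow-up in both arms is at 6 weeks.

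Between visits, "For the first 6 weeks of the study, all patients will receive a weekly Compliance Survey". The four items listed for it all concern adherence to the conservative regimen. Patients are also reminded to contact the study physicians about adverse events.

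Section d (Recording and Reporting Adverse Events) lists local events to be recorded, among them rash, injection-site pain, heat, swelling, knee pain and erythema.

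**The concern.** Knee pain and swelling are on the list of local events, and every patient enters with a symptomatic knee, so these events can arise in either arm without an injection. If one arm is asked more often in the first six weeks, its recorded rate can differ for that reason alone. Patients, parents and the injecting physician know the assignment, which makes unequal questioning harder to discount.

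A separate issue is sensitivity. Injection reactions can be brief: in the hip osteoarthritis study that the protocol cites, "Ten patients reported a slight pain during or after the injection, which spontaneously resolved in 1 or 2 days", out of 20 treated. A reaction of that length to the third injection would be over well before a visit three weeks later.

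The stake is the descriptive safety profile by arm. The plan says this study has never been done in children, and with 12 patients per arm a few differently captured events change the reported rates. No efficacy endpoint is affected.

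**Working it through.** **Visit counts.** PRP: 3 injection visits + 5 follow-ups (6 weeks, 12 weeks, 6, 9 and 12 months) = 8, or 9 with separate consent. Controls: 5 follow-ups, or 6 with separate consent. This reproduces the stated 8 and 5. The control narrative, however, counts one initial visit plus visits 2 to 5, which leaves only four follow-ups against five in the schedule.

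**Assessments up to week 6, at-each-visit rule.** The week-1 examination precedes any injection, and a control may also have a baseline contact then, because consent and baseline can be combined. The certain surplus is therefore weeks 2 and 3. After week 1 through week 6, PRP has 3 assessments (weeks 2, 3, 6) and controls have 1 (week 6).

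**Assessments up to week 6, follow-up-visit rule.** Each arm has 1 (week 6). Equality is restored, but a reaction to the first injection then waits nominally 6 − 1 = 5 weeks, or 35 days.

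**Gap after the third injection, both rules.**
- Nominal: week 6 − week 3 = 21 days.
- With ±10 days on the injection and ±1 week on the visit: 21 − 10 − 7 = 4 to 21 + 10 + 7 = 38 days.
- With the ±7-day injection window also printed in Table 3: 21 − 7 − 7 = 7 to 21 + 7 + 7 = 35 days.
- If the 6-week visit is counted from the injections, as the clinical follow-up text can be read: about 42 days.

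**What unequal visits could do.** The plan states no recall period, so recall is an assumption, shown over a range. Take week 1 as day 0 and week 6 as day 35, with assessments at days 7, 14 and 35 (PRP) and day 35 (controls). Coverage is the number of distinct days within the recall window of an assessment, divided by 35.

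| Assumed recall | PRP | Control |
|---|---|---|
| 2 days | 6/35 = 17% | 2/35 = 6% |
| 7 days | 21/35 = 60% | 7/35 = 20% |
| 14 days | 28/35 = 80% | 14/35 = 40% |
| Full | 35/35 = 100% | 35/35 = 100% |

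Under the follow-up-visit rule, the control column applies to both arms.

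**With the survey used.** Weekly questions with 7-day recall at days 7, 14, 21, 28 and 35 cover 5 × 7 = 35 of 35 days in both arms, if all are answered. A reaction to the third injection would be asked about nominally 7 days later.

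**The case against.** Several points on the other side stand.

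- A reader might infer that PRP patients have no contact after the third injection. They do: the weekly survey runs through week 6, they receive a post-injection handout, and they are reminded to report events. What is absent is a scheduled visit and a documented adverse event question.
- A reader might infer that short reactions are missed. Onset, duration and outcome are to be recorded, so an event that has resolved can still be entered from memory. Reactions to injections 1 and 2 can be asked about at the next injection visit, nominally a week later. The risk is under-recall, chiefly for injection 3. The 1-to-2-day duration comes from hip patients with a mean age of 52, not from adolescent knees.
- A reader might infer that PRP is bound to show more events. Extra visits push PRP counts up, while the gap after injection 3 pushes them down. In that gap neither arm has a visit, so it is a loss of sensitivity rather than an inequality.
- No between-arm safety test is planned, and relatedness is judged for each event. This limits the harm, but rates set side by side are still affected by unequal questioning.
- The survey form is an attachment not included in the documents, so an adverse event item on it cannot be ruled out.

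Extra visits come with comparing injection with no injection. That explains the imbalance but does not prevent asking both arms the same questions on the same dates.

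**Conclusion.** The point holds as a cheap improvement to safety collection. The two rules conflict, and each leaves a weakness: three assessments against one in the early weeks, or equal numbers with the injection weeks uncovered. Under both, reactions to the third injection depend on recall over nominally 21 days (4 to 38) or on the family calling.

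Descriptive rates by arm may be distorted, but neither the direction nor the size can be fixed from the documents. The 60% against 20% figure rests on an assumed 7-day recall and the at-each-visit rule; with full recall the difference disappears. A starker illustration is possible: with an assumed 10% chance of a recorded event per contact, independent across contacts, 1 − 0.9³ = 27% of PRP patients against 10% of controls would have one. At 5% it is 14% against 5%, and at 20% it is 49% against 20%. These figures follow wholly from the assumption, and they give a control visit that looks back five weeks the same yield as a PRP visit that looks back one. They should not be read as an estimate of bias.

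**What to change.** 1. Reconcile section c with Safety Measurements, so that one rule states at which visits adverse events are assessed. In the same edit, reconcile the two printed injection windows and the control visit count.
2. Add to the weekly survey (weeks 1 to 6, both arms) a short fixed checklist: the local events in section d, fever, and pain medication taken, with a one-week recall period. Existing study personnel review the answers and pass positive ones to the study physicians. If the attached form already asks this, say so in Safety Measurements.
3. Base between-arm summaries on the survey and the visits common to both arms. List events found only at injection visits separately for PRP.
4. Define the medication-recording period for controls; it is now anchored to the last injection, which they do not have.

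No visit is added. The cost is slightly more response burden, staff time to review answers, and more minor events recorded in both arms.

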## **Data Analysis Plan**

The anatomical location of osteochondritis dissecans will be documented for each patient on each of two MRI scans. Mean T1 values with dGEMRIC imaging **will be measured by two separate pediatric radiologists** at the site of cartilage pathology, adjacent to the site of pathology within the cartilage, and distant to the site of pathology within the cartilage on both initial and follow up imaging. Di Paola classification [33] will be used on the diagnostic imaging sequences to score the lesion pre-inoculation and on post-inoculation imaging.

### **Proposed statistical analysis for Aim 1: Cartilage healing**

The T1GD value on dGEMRIC measures GAG content in cartilage. Higher T1GD values are associated with higher GAG content in the tissue, a positive measure of cartilage health. We assume that the value is approximately normal.

We plan to fit a general linear mixed model [39] for the outcome of T1GD. Predictors will include the visit at which the T1GD test was performed (initial MRI and 6 months), whether the site was weight bearing or not, and whether the side was affected or not, and the treatment group. Age will be included as a covariate. An unstructured covariance will be used to account for correlation between T1GD measurements on the same participant. Jackknifed-studentized residuals will be examined to assess normality, and transformations will be applied as appropriate.

We will test the null hypothesis of no time by treatment by weight bearing surface by affected side interaction. Given a non-significant interaction, we will test the main effects of time and treatment, comparing the difference between the weight-bearing and non-weight bearing surface for the affected and non-affected sides. Estimates, 95% confidence intervals, and p-values will be produced. All hypothesis tests will be performed using the Wald test with Kenward and Roger degrees of freedom[40] . Hypothesis tests will be performed at the Bonferroni corrected alpha of  $0.05/3 = 0.017$ .

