#### **Description of Population to be Enrolled:**

This study aims to enroll 24 subjects, 12 patients for each of the two treatment arms, all with documented stable juvenile osteochondritis dissecans identified via imaging. We believe 24 patients could be included during the time period allotted for the study based on the number of patients suffering from OCD seen annually at the Children's Hospital Sports Medicine Clinic.

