#### **Patient Recruitment**

A diagnostic knee MRI (through CHCO or an outside facility) will have been performed as standard of care prior to study participation, utilizing dGEMRIC, a Non-contrast MRI or a MRI with and without contrast in patients with a high clinical suspicion for osteochondritis dissecans. The study is posted on the clinicaltrials.gov website and patients and/or their parents may call and inquire about eligibility.

Lesions will be classified according to Di Paola et al classification [33]

This uses 5 stages as follows:

Grade 1: Small change of signal without clear margins of fragment,

Grade 2: osteochondral fragment with clear margins but without fluid between fragment and underlying bone,

Grade 3: fluid is visible partially between fragment and underlying bone,

Grade 4: fluid is completely surrounding the fragment, but the fragment is still in situ;

Grade 5: fragment is completely detached and displaced.

Only patients with Di Paola stage 1 or 2 lesions will be approached for study participation and consented into the study.

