### **Power Analysis**

We conducted a power analysis for Aim 1, the primary endpoint of the study. The maximum sample size for the proposed trial is fixed at 12 patients per arm (24 participants total). The sample size is limited due to costs associated with dGEMRIC.

We calculated power for the test of no difference in T1GD between the treatment groups. We assumed a standard deviation of 50 ms for T1GD values, and a correlation of 0.2 between the baseline MRI and the 12-month T1GD measurements. Estimates were based on T1GD values reported by Neuman et al[42]. We expect T1GD values to be 85 ms higher in the injection group when compared to conservative therapy at the 6 month time point with no difference at baseline. We calculated power for 10, 11, or 12 participants per arm. Power was calculated using GLIMMPSE version 2.0.1.[43]

To detect a mean difference of 85 ms in T1GD between the treatment groups, power will be 0.93 with a Type I error rate of 0.05, for 12 participants per treatment group. To ensure a conclusive study, we will target an effective sample size of 10 participants per group. Over the 12 months, we expect to lose up to two participants per treatment group. To account for the attrition, we have set an enrollment goal of 24 participants, or 12 participants per treatment group.

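### Aim 1 models baseline and 6-month T1GD as outcomes with no baseline adjustment; using the baseline as a covariate would gain precision at no data cost

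*Combined protocol and SAP*

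**What the plan says.** The Aim 1 analysis section specifies a general linear mixed model for T1GD: "Predictors will include the visit at which the T1GD test was performed (initial MRI and 6 months"). The other predictors are weight-bearing surface, affected side and treatment group. Age is the only covariate and the covariance is unstructured. The first test is the four-way interaction of time, treatment, surface and side, at alpha 0.05/3 = 0.017. No baseline covariate and no equality of baseline means is written.

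The baseline scan comes before randomisation. Patient Recruitment says that the diagnostic MRI "will have been performed as standard of care prior to study participation". The inclusion criteria date it to the 3 months before consent, and the Randomization section opens the envelope after consent.

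The Power Analysis uses these inputs: "We assumed a standard deviation of 50 ms for T1GD values"; "a correlation of 0.2 between the baseline MRI and the 12-month T1GD measurements"; and "We expect T1GD values to be 85 ms higher in the injection group" than under conservative therapy, "at the 6 month time point with no difference at baseline". It states power 0.93 at a type I error of 0.05 with 12 per arm, and an effective target of 10 per arm.

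**The concern.** Because the baseline scan precedes randomisation, the arms have equal expected T1GD at baseline, and the power section assumes this ("with no difference at baseline"). A conventional model for the four-way test contains all lower-order terms, including a treatment difference at baseline. Each arm then gets its own baseline mean, and a time-by-treatment contrast subtracts one noisy baseline difference from the 6-month difference. When baseline and follow-up are weakly correlated, this subtraction adds more noise than it removes.

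What is at stake is precision in a trial fixed at "12 patients for each of the two treatment arms". The Power Analysis says that dGEMRIC cost limits enrolment, so the lost precision cannot be bought back with more patients.

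**Working it through.** **Inputs.** SD 50 ms, correlation r = 0.2 (stated for 12 months; applied here to the 6-month endpoint), effect 85 ms at 6 months and 0 at baseline, 12 or 10 per arm (all from Power Analysis). Alpha is 0.05 (Power Analysis) or 0.05/3 = 0.0167 (Aim 1 analysis). Tests are taken as two-sided, which the documents do not state. Power is from the noncentral t distribution.

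**The stated 0.93.** With 12 per arm, the readings tried were:

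| Contrast | Alpha | Power |
|---|---|---|
| Change from baseline | two-sided 0.05 | 0.882 |
| 6 months only | two-sided 0.05 | 0.978 |
| Baseline-adjusted | two-sided 0.05 | 0.982 |
| Joint 2-df test of both visits | 0.05 | 0.952 |
| Treatment effect averaged over visits (42.5 ms) | two-sided 0.05 | 0.729 |
| Change from baseline | one-sided 0.05 | 0.939 |
| 6 months only | two-sided 0.0167 | 0.932 |

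No two-sided reading at 0.05 gives 0.93. The two that come close point in opposite directions: one includes the baseline noise and the other does not. The basis of 0.93 is therefore not identified.

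**Variance of the lesion-site contrast.**
- Change score: 2(1 - r) = 2(0.8) = 1.60, so SD = 50 × √1.60 = 63.2 ms. With 12 per arm, SE = 63.2 × √(2/12) = 25.8 ms.
- Baseline as covariate: 1 - r² = 1 - 0.04 = 0.96, so SD = 50 × √0.96 = 49.0 ms and SE = 49.0 × √(2/12) = 20.0 ms.
- Variance ratio: 0.96/1.60 = 0.60, in general (1 + r)/2. This treats the slope on baseline as known.

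**Power for 85 ms at the lesion site, two-sided.** The adjusted column gives the formula with 1 df lost for the slope, then a simulation of 20,000 trials with the slope estimated.

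| Per arm | Alpha | Change score | Same-site baseline as covariate |
|---|---|---|---|
| 12 | 0.05 | 0.88 | 0.98 / 0.98 |
| 12 | 0.0167 | 0.75 | 0.94 / 0.93 |
| 10 | 0.05 | 0.81 | 0.95 / 0.94 |
| 10 | 0.0167 | 0.64 | 0.88 / 0.85 |

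**Planned four-way test.** If the between-site correlations have the same pattern within and across visits, the ratio is again 0.60. Absolute power needs between-site correlations that the documents do not give. Assume SD 50 at each site, the full 85 ms in the contrast, within-visit between-site correlation from 0 to 0.8, and cross-site cross-visit correlation from 0 to 0.2. Power at alpha 0.0167 with 12 per arm then runs from about 0.20 to 0.75 unadjusted and from 0.34 to 0.97 with baseline used and the covariance taken as known.

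**Which form of adjustment.** Four sites at two visits give an 8 × 8 unstructured covariance with 8 × 9/2 = 36 parameters, from at most 24 patients. With complete data, constraining the baseline means under that covariance amounts in effect to adjusting for all four baseline values with estimated slopes. Simulated variance relative to the change score (assumed between-site correlation 0.3, 12 per arm):

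| r | Same-site or same-contrast covariate | Equal baseline means, unstructured |
|---|---|---|
| 0.2 | about 0.61-0.64 | about 0.71-0.75 |
| 0.6 | about 0.85 | about 1.0 |
| 0.8 | about 0.93-0.95 | about 1.1 |

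For the constrained form at r = 0.2 and alpha 0.0167, lesion-site power is about 0.87 with 12 per arm and 0.74-0.75 with 10.

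**The case against.** The strongest reply is that the planned model is unbiased, so this is an efficiency preference. That stands, and nothing here says the analysis is invalid.

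A reader might infer that this feature pulls power below the stated 0.93. The documents do not support that. The Power Analysis names neither contrast nor sidedness, and a one-sided change-score contrast gives 0.939, so the figure may already include the baseline noise. The drop from 0.88 to 0.75 comes from the stricter alpha alone. Adjustment does not guarantee 0.93 either: with the plan's effective 10 per arm it reaches about 0.85-0.88 at alpha 0.017.

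A reader might also take equal baseline means and a baseline covariate as interchangeable, or assume that adjustment can never lose. Neither holds under the planned unstructured covariance, as the last table shows.

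Four limits remain:
- Separate baseline means are inferred from the interaction test, not written out.
- The 0.60 ratio applies to time-by-treatment contrasts, not directly to the step-down main effects. The lesion-site contrast used for the power figures is not one that the plan names.
- Under the 6-month research MRI rules, only patients diagnosed by dGEMRIC have dGEMRIC again, so 12 T1GD pairs per arm is not assured.
- Equality at baseline holds for all randomised patients. It could fail if those who leave on learning their assignment are not analysed.

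**Conclusion.** The point holds as a free improvement. At the plan's SD and correlation, the same-site baseline covariate removes about 40% of the variance of a time-by-treatment contrast in theory (1 - 0.60), and about 36-39% with the slope estimated at 12 per arm. In lesion-site power at the planned alpha, that is 0.75 to 0.93-0.94 with 12 per arm and 0.64 to about 0.85-0.88 with 10.

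The size rests on r = 0.2 carrying over from 12 to 6 months, two-sided tests and complete T1GD pairs. The gain shrinks as r rises: the theoretical ratio is 0.70 at 0.4 and 0.80 at 0.6, and estimating the slope could cancel it at very high correlation. The four-way test gains in the same proportion if its contrast also has correlation 0.2 between visits, but its absolute power cannot be fixed from the documents.

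**What to change.** In the Aim 1 analysis section, make the 6-month T1GD contrast the outcome, with the corresponding baseline T1GD as covariate (same site, or the same contrast of sites), along with age and treatment group. By the MRI rules, patients assigned a 6-month dGEMRIC had a diagnostic dGEMRIC, so the covariate needs no new scan.

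If a longitudinal model is preferred, let treatment terms enter at 6 months only, so that baseline means are equal across arms, and replace the unstructured covariance with a more parsimonious one fixed in advance. Under the unstructured form it gains less, and it can lose precision once the correlation is about 0.6 or higher.

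In the Power Analysis, name the contrast, state that it is two-sided, and give power at alpha 0.017 for 10 and 12 per arm, with the baseline correlation tied to 6 months. The cost is a few sentences and a few lines of code, settled before unblinding.
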